6.2 Dose reductions for AEs of interest in patients taking dabrafenib and trametinib

6.2.1 Plantar- Palmar Erythrodysesthesia (Hand foot syndrome, PPES) – Measures for PPES should include:

Lifestyle modification: avoidance of hot water; traumatic activity; constrictive footwear; or excessive friction on the skin. Adopt the use of thick cotton socks and gloves, and shoes with padded insoles.

Symptomatic treatments: apply moisturizing creams frequently; topical keratolytics (eg, urea 20 to 40% cream; salicylic acid 6%; tazarotene 0.1% cream; fluorouracil 5% cream), clobetasol propionate 0.05% ointment for erythematous areas; topical lidocaine 2%; and/or systemic pain medication such as nonsteroidal anti-inflammatory drugs (NSAIDs); codeine; and pregabalin for pain.

Dose modification may also be required.

6.2.2 Pancreatitis

In the event of abdominal pain or suspected pancreatitis, amylase and lipase laboratory samples should be collected for confirmation of the diagnosis. Patients should be closely monitored when re-starting dabrafenib after an episode of pancreatitis.

6.2.3 Uveitis and ocular events (see below for specific guidelines)

Ophthalmological exams will be required at baseline, Week 6 and annually thereafter. Episodes of visual changes have been observed in subjects receiving trametinib, dabrafenib, and combination therapy. An ophthalmologist should be consulted if changes in vision develop. However, if the visual changes are clearly unrelated to study treatment (eg, allergic conjunctivitis), then monitor closely as it may be reasonable to defer ophthalmic examination.

Treatment with dabrafenib has been associated with the development of uveitis, including iritis. Monitor patients for visual signs and symptoms (such as, change in vision, photophobia and eye pain) during therapy. Special attention should be given to retinal findings (eg, retinal pigment epithelial detachment (RPED) or retinovascular abnormalities (ie, branch or central retinal vein occlusions (RVO)). Guidelines regarding management and dose reduction for visual changes and/or ophthalmic examination findings considered to be related to study treatment are provided in the below tables:

Table 5: Management and Dose Modification Guidelines for Visual Changes and/or Ophthalmologic Examination Findings

CTCAE Grade ^a	Adverse Event Management	Action and Dose Modification
Grade 1 ^b	
 Consult ophthalmologist within 7 days of onset 	
 If dilated fundus examination cannot be performed within 7 days of onset, interrupt trametinib until RPED and RVO can be excluded by retina specialist/ophthalmologist. If subject is receiving trametinib/dabrafenib combination therapy dabrafenib may be continued If RPED and RVO excluded, continue (or restart) trametinib at same dose level If RPED suspected or diagnosed: see RPED dose modification table Y below; report as SAE if diagnosed If RVO diagnosed: Permanently discontinue trametinib and report as SAE
Grade 2 and Grade 3	
 Consult ophthalmologist immediately Interrupt trametinib. If subject is receiving trametinib/dabrafenib combination therapy dabrafenib may be continued 	
 If RPED and RVO excluded, restart trametinib at same dose level If RPED diagnosed, see RPED dose modification table below; report as SAE If RVO diagnosed: Permanently discontinue trametinib and report as SAE
Grade 4	
 Consult ophthalmologist immediately Interrupt trametinib. If subject is receiving trametinib/dabrafenib combination therapy dabrafenib may be continued 	
 If RPED and RVO excluded, may consider restarting trametinib at same or reduced dose after discussion with study medical monitor If RVO or RPED diagnosed, permanently discontinue trametinib and report as SAE

c. Refers to CTCAE Version 4.0 ‘Eye disorders – Other, specify’

d. If visual changes are clearly unrelated to study treatment (eg, allergic conjunctivitis), monitor closely but ophthalmic examination is not required.

Table 6: Recommended dose modifications for trametinib for retinal pigment epithelial detachments (RPED)

CTCAE Grade ^a	Action and Dose Modification
Grade 1 RPED (Asymptomatic; clinical or diagnostic observations only)	
 • Continue treatment with retinal evaluation monthly until resolution. If RPED worsens follow instructions below
Grade 2-3 RPED (Symptomatic with mild to moderate decrease in visual acuity; limiting instrumental ADL)	
 • Interrupt trametinib • Retinal evaluation monthly • If improved to \leq Grade 1, restart trametinib at lower dose (reduced by 0.5 mg) or discontinue in patients taking trametinib 1 mg daily

e. Refers to CTCAE Version 4.0 ‘Retinopathy’

6.2.4 Hyperglycemia

Hyperglycemia requiring an increase in the dose of, or initiation of insulin or oral therapy can occur with dabrafenib. Monitor serum glucose levels as clinically appropriate during treatment with dabrafenib in subjects with pre-existing diabetes or hyperglycemia. Advise patients to report symptoms of severe hyperglycemia such as excessive thirst or any increase in the volume or frequency of urination.

Investigators should always err on the side of caution in these settings if treatment-related toxicity is a possibility.

6.2.5 Pyrexia

Episodes of pyrexia have been observed in subjects receiving dabrafenib monotherapy, and is increased in incidence and severity in subjects receiving dabrafenib in combination with trametinib. In a minority of cases the pyrexia was accompanied by symptoms such as severe chills; dehydration; hypotension; and dizziness or weakness.

Subjects should be instructed on the importance of immediately reporting febrile episodes. In the event of a fever, the subject should be instructed to take anti-pyretics (eg, ibuprofen or acetaminophen) as appropriate to control fever. The use of oral corticosteroids should be considered in those instances in which anti-pyretics are insufficient. Monitor serum creatinine and other evidence of renal function during and following severe events of pyrexia.

Guidelines regarding management and dose modifications for pyrexia considered to be related to study treatment provided below.

Table 7: Management and Dose Modification Guidelines for Pyrexia

Adverse Event	Adverse Event Management	Action and Dose Modification
Pyrexia: ^a	
All Events:
 
 • Clinical evaluation for infection and hypersensitivity ^c • Laboratory work-up ^c • Hydration as required ^d 
1st Event ^b:
 
 • Administer anti-pyretic treatment as clinically indicated and initiate prophylactic treatment if associated with rigors, renal failure, dehydration or hypotension ^c 
2nd Event ^f
 
 • Within 3 days of onset of pyrexia 
 ○ Optimize anti-pyretic therapy ○ Consider oral corticosteroids (ie, prednisone 10 mg) for at least 5 days or as clinically indicated ^f 
Subsequent Events:
 
 • Within 3 days of onset of pyrexia: 
 ○ Optimize oral corticosteroid dose as clinically indicated for recalcitrant pyrexia ^f ○ If corticosteroids have been tapered and pyrexia recurs, restart steroids ○ If corticosteroids cannot be tapered consult medical monitor 	
1st Event:
 
 • Interrupt dabrafenib • Continue trametinib • Once pyrexia resolves to baseline, restart dabrafenib at the same dose level 
 ○ If fever was associated with rigors, renal failure, dehydration or hypotension, reduce dabrafenib by one dose level ^g 
2nd Event:
 
 • Interrupt dabrafenib • Continue trametinib • Once pyrexia resolves to baseline, restart dabrafenib at the same dose level 
 ○ If fever was associated with rigors, renal failure, dehydration or hypotension, reduce dabrafenib by one dose level ^g 
Subsequent Events:
 
 • Interrupt dabrafenib • Continue trametinib • Once pyrexia resolves to baseline, restart dabrafenib reduced by one dose level ^g • If dabrafenib must be reduced to < 50 mg BID, permanently discontinue dabrafenib. Trametinib may be continued

- a. Pyrexia is defined as a body temperature equal to or above 38.5 Celsius or 101.3°Fahrenheit.
- b. For subjects experiencing pyrexia complicated by rigors, severe chills, etc., a clinical evaluation and laboratory work-up is mandatory for each event; anti-pyretic treatment should be started immediately at the first occurrence and prophylactic anti-pyretic treatment is recommended
- c. Thorough clinical examination for signs and symptoms of infection or hypersensitivity is required; laboratory work-up should include full-blood-count, electrolytes, creatinine, blood urea nitrogen (BUN), C-reactive protein (CRP), liver-function tests, blood culture, and urine culture.
- d. Oral hydration should be encouraged in subjects without evidence of dehydration. Intravenous hydration is recommended in subjects experiencing pyrexia complicated by dehydration/hypotension.
- e. Anti-pyretic treatment may include acetaminophen, ibuprofen, or suitable anti-pyretic medication according to institutional standards. Prophylactic anti-pyretic treatment may be discontinued after three days in the absence of pyrexia
- f. In subject experiencing pyrexia complicated by rigors, severe chills, etc., which cannot be controlled with anti-pyretic medication, oral corticosteroids should be started at the 2nd event and doses should be gradually increased for subsequent events.
- g. Dabrafenib should be reduced by one dose level after three episodes of pyrexia complicated by rigors, severe chills, etc., which cannot be managed by best supportive care and increasing doses of oral steroids. Escalation of dabrafenib is allowed if no episode of pyrexia is observed in the 4 weeks subsequent to dose reduction.

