6.2.9 Renal Insufficiency

Cases of renal insufficiency have occurred in subjects receiving dabrafenib and the combination of dabrafenib and trametinib. Prior to start of study treatment, concomitant medications should be reviewed for the potential risk of inducing nephrotoxicity and concomitant medications should be modified if clinically possible. Guidelines regarding management and dose reduction for renal insufficiency considered to be related to study treatment by the investigator are provided below.

Table 8: Management and Dose Modification Guidelines for Renal Insufficiency

Serum Creatinine Level	Adverse Event Management	Action and Dose Modification
Serum creatinine increase > 0.2 mg/dL (18 umol/L) but ≤ 0.5 mg/dL (44 umol/L) above baseline	
 • Recheck serum creatinine within 1 week • Serum creatinine increase > 1 week: contact Novartis Medical Monitor. If elevation persists beyond 4 weeks, recommend evaluation (consider renal biopsy) for etiology; consider nephrology consultation. • If pyrexia is present, treat pyrexia as per guidelines ^a 	
 • Continue study treatment at the same dose level
Serum creatinine increase > 0.5 mg/dL (44 umol/L) above baseline or serum creatinine >2 mg/dL (> 177 umol/L)	
 • Monitor serum creatinine ≥ 2 times per week • Hospitalization may be necessary if serum creatinine cannot be monitored frequently • If pyrexia is present, treat pyrexia per guidelines ^a • Consult nephrologist if clinically indicated • Perform renal biopsy if clinically indicated, for example: 
 ○ Renal insufficiency persists despite volume repletion ○ Subject has new rash or signs of hypersensitivity (such as elevated eosinophil count) 	
 • Interrupt study treatment until serum creatinine recovers to baseline • Restart with study treatment ^b

a. NSAIDs can induce renal insufficiency, especially in subjects with dehydration; encourage oral fluids or consider intravenous fluids as clinically indicated. See guidelines for pyrexia Section

b. Investigator may restart at either the same or a reduced dose level. Escalation of study treatment to previous dose level is allowed if another episode of renal insufficiency does not occur after 4 weeks of dose reduction.

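### For a treatment-related fever with renal failure that meets Table 8's higher creatinine row, Table 7 continues trametinib while Table 8 interrupts study treatment, and nothing says which table governs

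*Combined protocol and SAP*

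**What the plan says.** All places are in the combined protocol and SAP.

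**Section 6.2.5, Table 7** covers pyrexia considered related to study treatment. For 1st, 2nd and subsequent events alike, dabrafenib is held and the trametinib instruction is "Continue trametinib". Dabrafenib resumes when the fever is back to baseline. At the 1st and 2nd events the restart is at the same level, with one exception: "If fever was associated with rigors, renal failure, dehydration or hypotension, reduce dabrafenib by one dose level". That line carries marker g. Footnote g reads "Dabrafenib should be reduced by one dose level after three episodes of pyrexia complicated by rigors, severe chills, etc", and limits this to episodes that supportive care and rising steroid doses have not controlled.

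**Section 6.2.9, Table 8** has this scope: "Guidelines regarding management and dose reduction for renal insufficiency considered to be related to study treatment by the investigator are provided below". Its higher row applies to a creatinine rise of more than 0.5 mg/dL above baseline, or a value above 2 mg/dL. The action column of that row says "Interrupt study treatment until serum creatinine recovers to baseline". Footnote b adds: "Investigator may restart at either the same or a reduced dose level". The management column of the same row says "If pyrexia is present, treat pyrexia per guidelines".

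**The end of section 6.1** describes the dose-modification guidance as general and asks investigators to apply clinical judgment. It gives no order of precedence among the tables.

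**The concern.** The protocol expects fever and renal impairment to occur together. Table 7 lists renal failure as a complication of fever, Table 8's higher row mentions pyrexia, and section 6.2.5 asks for renal function to be monitored during and after severe fever. A site facing this event would find itself in both tables at once.

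The two tables then give opposite instructions for trametinib, and different instructions on when dabrafenib restarts and at what dose. At stake is a safety instruction for an event the protocol itself foresees. Two sites could each follow the protocol to the letter, one keeping the patient on trametinib and the other stopping it.

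**Working it through.** No arithmetic applies, because the point rests on no sample size, error rate or event count. The check is a comparison of the two action columns for one patient: fever and renal insufficiency both judged treatment-related, with creatinine in Table 8's higher row.

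| Action | Table 7 (fever with renal failure) | Table 8 (higher row) | Can both be followed? |
|---|---|---|---|
| Trametinib during the event | Continue | Interrupt, if study treatment includes trametinib | No |
| Dabrafenib during the event | Interrupt | Interrupt, if study treatment includes dabrafenib | Yes |
| Trigger for restart | Fever resolved | Creatinine back to baseline | Yes, by waiting for the later of the two |
| Dabrafenib dose at restart (1st or 2nd event) | One level lower, subject to footnote g | Same or lower, investigator's choice | Yes, by a one-level reduction |

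**Step 1: does the event fall in both tables?** Table 7 does not define renal failure. Its correspondence to Table 8's creatinine thresholds is therefore an inference, though a natural one given the cross-reference "If pyrexia is present, treat pyrexia per guidelines". The point is confined to the higher row. The lower row (rise above 0.2 and up to 0.5 mg/dL) continues study treatment, so trametinib is not in dispute there.

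**Step 2: which drugs does study treatment mean in Table 8?**
- Both drugs: the trametinib instructions contradict each other.
- Trametinib only: they still contradict each other.
- Dabrafenib only: the contradiction disappears.

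The both-drugs reading is the best supported. Section 6.2.9 opens with cases on dabrafenib and on the combination, and Tables 5, 6, 7 and 11 name a single drug where only one is meant. Usage is not perfectly uniform. In Table 10 the Grade 3 row interrupts trametinib and then speaks of restarting study treatment. That is a further reason for Table 8 to name the drugs.

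**Step 3: is there a tie-break?** The reference from Table 8 to the pyrexia guidelines sits in the management column and concerns treatment of the fever. It leaves the interruption in the action column standing. Table 4 applies only where no specific guideline does. Section 4 says trametinib may continue when dabrafenib is interrupted, which is a permission and not a ranking of tables. None of these settles the matter.

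**Step 4: the two weaker differences.** On the restart trigger and restart dose, one course of action could satisfy both tables, but no text directs it. Table 8 also allows the same-dose restart that Table 7's complicated-fever branch excludes. That branch is itself unclear, since the table cell applies the reduction from the 1st event and footnote g applies it after three episodes.

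**The case against.** The strongest reply is that the tables are organised by toxicity. On that view, Table 7's trametinib line means only that fever alone is no reason to stop the drug. Table 8 then decides what to do about creatinine, and a patient in its higher row has study treatment held whatever Table 7 says. Section 6.1's appeal to clinical judgment supports reading the tables flexibly.

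This would settle a fever in which renal function is merely coincidental. It does not settle this case, because Table 7 addresses fever with renal failure by name and changes only the dabrafenib dose, leaving trametinib running. The clinical-judgment statement softens the consequence but does not choose between the tables.

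Three parts of the reply stand. First, a reader might infer that the tables are incompatible on every action. They are not: only the trametinib instruction strictly clashes. Second, if footnote g qualifies the Table 7 reduction, no reduction is mandatory at a 1st or 2nd event and the dose difference there falls away. Third, the reach of renal failure and the meaning of study treatment are both inferred.

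**Conclusion.** The contradiction is real but narrow. For a treatment-related fever with renal failure that also meets Table 8's higher row, trametinib is both continued and interrupted, with no rule of precedence. The restart trigger and restart dose are secondary: they differ, can be reconciled, and are not reconciled in the text. The conclusion assumes that Table 7's renal failure can reach Table 8's thresholds and that study treatment in Table 8 includes trametinib.

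No size is attached. The protocol's Table 14 gives pyrexia in 54% (pooled) and 57% (Trial 2) of patients on the combination, but no document gives the share of fevers with renal failure. Any count among the planned 11 to 21 patients would rest on an unsupported assumption.

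A reader might also infer that inconsistent handling would make the dose and interruption data non-comparable, or would distort the section 12.5 review of 6-week completion against its two-thirds threshold. The documents do not support that. The frequency is unknown, the trial has a single arm, and section 12.5 already accommodates dose modifications made under section 6. The case for a change rests on clear safety instructions for an anticipated event.

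**What to change.** Reconcile Tables 7 and 8 for fever with a creatinine rise that meets Table 8's higher row:

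- State which table governs when both apply.
- Name the drug or drugs meant by study treatment in Table 8.
- Tie renal failure in Table 7 to Table 8's creatinine criteria, so that a site can tell when the event falls in both tables.
- Give one restart condition and one restart-dose rule for the combined event, cross-referenced in both tables and consistent with footnote g.

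Which clinical rule to adopt is for the sponsor and investigator; this point takes no position. The cost is the wording of two tables in the next amendment, with the review-board approval at each site that section 11.1 requires of any amendment. No visits, tests or patients are added.

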6.0 DOSE MODIFICATIONS

6.1 Dose Modification for General Toxicities

General guidelines regarding management and dose reduction for adverse events that are considered by the investigator to be related to study treatment and for which specific guidelines do not apply are provided in the table below. These guidelines are intended primarily for toxicities not easily managed with routine supportive care. For example, alopecia is not an indication for dose modification, nor is grade 2 nausea and vomiting that can be easily managed with anti-emetics.

Table 3: Recommended dabrafenib and trametinib dose level reductions

DABRAFENIB		TRAMETINIB	
Dose Level	Dose/Schedule	Dose Level	Dose/Schedule
Full dose	150 mg twice daily	Full dose	2 mg once daily
First reduction	100 mg twice daily	First reduction	1.5 mg once daily
Second reduction	75 mg twice daily	Second reduction	1 mg once daily
Third reduction	50 mg twice daily	Third reduction	0.5 mg once daily

Table 4: Dose Modification Guidelines - General

CTCAE Grade	Occurance	Action and Dose Modification ^{a,b}
Grade 1 or Grade 2 (tolerable)	N/A	Continue study treatment at same dose level (no dose modification) and monitor as clinically indicated
Grade 2 (Intolerable) or Grade 3	1 st , 2 nd or 3 rd occurrence	Interrupt study treatment until toxicity resolves to ≤ grade 1 then restart at next lower dose level
	4 th or greater occurrence	Discontinue treatment
Grade 4	1 st occurrence	Interrupt study treatment until toxicity resolves to ≤ grade 1 or baseline then restart at next lower dose level or discontinue at discretion of investigator
	2 nd occurrence	Interrupt study treatment until toxicity resolves to ≤ grade 1 or baseline then restart at two dose levels lower than the starting dose or discontinue at discretion of investigator and after discussion with the medical monitor.
	3 rd occurrence	Discontinue treatment

- a. Treatment should be discontinued if more than 3 dose reductions are required
- b. Approval from the protocol PI is required to restart study treatment after ≥ 21 days

When an individual’s adverse reactions are under effective management, dose re-escalation following the same dosing steps as de-escalation may be considered.

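### Table 7 and its footnote g set different points for reducing dabrafenib after a fever with rigors, and the protocol does not say which governs

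*Combined protocol and SAP*

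**What the plan says.** Table 7 in protocol Section 6.2.5 handles fever by event number. Dabrafenib is interrupted and trametinib continues at every event.

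- **1st and 2nd events, uncomplicated:** "Once pyrexia resolves to baseline, restart dabrafenib at the same dose level".
- **1st and 2nd events, complicated:** "If fever was associated with rigors, renal failure, dehydration or hypotension, reduce dabrafenib by one dose level". The line is identical for both events and carries marker g each time.
- **Subsequent events:** "Once pyrexia resolves to baseline, restart dabrafenib reduced by one dose level", also marked g, with no requirement that the fever be complicated. The same cell adds: "If dabrafenib must be reduced to < 50 mg BID, permanently discontinue dabrafenib".

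Footnote g reads "Dabrafenib should be reduced by one dose level after three episodes of pyrexia complicated by rigors, severe chills, etc" and continues: "which cannot be managed by best supportive care and increasing doses of oral steroids". Its last sentence allows the dose to go back up after 4 weeks without fever. Footnote f, on complicated fever that anti-pyretics do not control, says "oral corticosteroids should be started at the 2nd event and doses should be gradually increased for subsequent events".

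The dose steps are in Section 6.1, Table 3, "Recommended dabrafenib and trametinib dose level reductions": dabrafenib 150, 100, 75 and 50 mg twice daily.

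**The concern.** A footnote normally states the condition under which the marked instruction applies. Here the marked instruction acts on one complicated fever, while the note names three complicated fevers plus failure of supportive care and steroids. A site that reads the table cell and a site that reads the note as its condition would restart the same patient on different doses.

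Two things are at stake. The first is a safety instruction for the event that Section 2.2 names as the most common on the combination. The second is consistency of treatment: up to 17 evaluable patients are treated across several institutions, and response is read at 6 weeks. If dabrafenib exposure before that read depends on which line a site follows, the dose behind the observed response rate is less well defined than the protocol intends.

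**Working it through.** The protocol states no figure for this point. The check sets the texts side by side and then walks down the dose ladder.

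**Step 1. Compare the triggers.**

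| | Table 7, 1st and 2nd event | Table 7, subsequent events | Footnote g |
|---|---|---|---|
| Event count | One | Third or later | After three |
| Complications | Rigors, renal failure, dehydration, hypotension | None required | Rigors, severe chills, and an open-ended remainder |
| Supportive care and steroids must have failed | No | No | Yes |
| Action | Down one level | Down one level | Down one level |

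Rigors are the only complication named in both lists, so a fever with rigors is the clean test case.

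**Step 2. Can footnote g's condition be met where marker g stands?** At a 1st or 2nd event there cannot yet have been three episodes. On footnote f's schedule steroids begin at the 2nd event, so at a 1st event they cannot have failed either. The condition cannot be satisfied on the 1st- and 2nd-event lines that carry the marker.

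**Step 3. Apply each text to successive fevers with rigors.** Inputs: the Table 3 ladder, no re-escalation and, for footnote g, episodes that supportive care and steroids do not control.

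| After fever with rigors no. | Table 7 action column | Footnote g as the trigger | Gap |
|---|---|---|---|
| 1 | 100 mg twice daily | 150 mg twice daily | 1 level |
| 2 | 75 mg twice daily | 150 mg twice daily | 2 levels |
| 3 | 50 mg twice daily | 100 mg twice daily | 2 levels |
| 4 | Below 50 mg: discontinue | No further step stated | – |

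At the first such fever the daily dose is 2 × 100 = 200 mg under one text and 2 × 150 = 300 mg under the other. The difference is (300 − 200) / 300 = 33%.

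**Step 4. How many patients could this touch?** Section 2.2 gives fever in 52% on the combination; Table 14 in Section 7.1.1 gives 54% (pooled) and 57% (Trial 2). Applied to 17 patients, 17 × 0.52 = 8.8 and 17 × 0.57 = 9.7. These are fevers of any kind, not limited to the first 6 weeks, in melanoma. Section 6.2.5 says only that a minority were complicated, so the affected number is smaller and cannot be derived from the documents. If grade 3–4 fever in Table 14 (5% to 7%) is taken as a stand-in for complicated fever, which is an assumption, the result is 17 × 0.05 = 0.85 to 17 × 0.07 = 1.2, or about one patient.

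**Step 5. Is the statistical design affected?** Recomputing the two-stage rule in Section 12.1 (stop if 0 of 9 respond; reject if 3 or more of 17 respond) gives type I error 0.0466, power 0.8122 and early stopping 0.630 under the null, all as stated. None of these depends on the fever rule.

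**The case against.** Footnote g does not say that three episodes are the sole ground for reduction, and it does not forbid an earlier one. A site that follows the table has also reduced by the third complicated fever. Marker g might have been meant for the re-escalation sentence, which fits all three marked lines, leaving the first sentence for recurrent fever that steroids do not control. The complication lists also differ. The table is headed as guidelines, and Section 6.1 leaves room for clinical judgment.

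Part of this stands. A reader might infer that footnote g permits reduction only after three episodes, or that no site could comply with both texts. The wording supports neither.

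The conflict nevertheless remains. Read as a separate later rule, the footnote's first sentence adds nothing: the table has already reduced at complicated events 1 and 2, and its subsequent-events line reduces for any fever. Its opening sentence describes the same one-level reduction it is attached to, and marker g appears three times, each time on a reduction line, so a stray marker is unlikely. The clinical-judgment sentence does not choose between the triggers.

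A reader might also infer that about 9 to 10 of 17 patients are affected, or that the conflict threatens the two-thirds completion rule in Section 12.5. The first figure counts all fevers. On the second, Section 12.5 treats Section 6 modifications as compatible with completing treatment, so a dose reduction is not non-completion. Discontinuation could count, but on the ladder above that needs a fourth complicated fever without re-escalation, and nothing in the documents suggests this is likely within 6 weeks.

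**Conclusion.** The point holds as an internal contradiction in a dose-management table. For a fever with rigors, the action column and its attached footnote imply restart doses one level apart at the first event (100 versus 150 mg twice daily) and two levels apart after the third (50 versus 100 mg twice daily). The third-event figure assumes no re-escalation and failure of supportive care and steroids. The subsequent-events line also disagrees with the footnote, because it reduces even for uncomplicated fever. No section says which text governs, so the same event may be dosed differently before the 6-week response read.

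The number of patients concerned is not known, and an effect on the response rate is possible but not shown. The statistical design figures are unaffected. The passages should be corrected because the instruction bears on safety and on uniform treatment in a small trial. This review takes no position on which rule is clinically right.

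**What to change.** Amend the Table 7 action column (1st, 2nd and subsequent events) and footnote g so that they state one and the same trigger for reducing dabrafenib. The text should settle three things: the event number, a single list of complications, and whether failure of supportive care and steroids is required. If footnote g was meant to carry only the re-escalation allowance, or to describe a separate situation, it should say so and its markers should be placed accordingly. The clinical choice belongs to the sponsor.

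The cost is an amendment to one table and its footnote, with notice to the sites. Sample size, decision rule and assessment schedule stay as they are. If patients have already been treated, listing each dabrafenib change for fever with its event number and complications would show whether sites followed different rules.
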